#### Study Purpose and Rationale:

Cerebrospinal fluid (CSF) shunts fail often, but diagnosis is difficult as symptoms are non-specific. Existing non-invasive tests are not able to assess flow directly but rely on secondary measures of shunt function. Conversely, invasive tests can be painful and risk contamination and infection of the shunt system.

This trial will evaluate the performance of FlowSense, a device for non-invasively assessing CSF shunt flow using thermal anisotropy measurements, in a prospective study setting. The objective of this study is to establish the performance of the device in subjects presenting with a possible shunt failure.

#### Study Design:

This is a prospective, open-label, blinded, multi-center, single-arm observational study of up to 150 (roll-in and main study) subjects at up to 10 trial sites. Patients with an existing CSF shunt and symptoms of a shunt failure will be recruited by the clinical investigators based on the inclusion and exclusion criteria.

Subjects will undergo evaluation with the FlowSense device and standard-of-care testing and will be followed for 7 days to determine if a revision was performed to repair or replace the existing shunt. In subjects undergoing a revision, intraoperative assessment of shunt functionality will establish the presence or absence of a complete shunt obstruction. FlowSense device data will be used to categorize shunt function as “flow confirmed” or “flow not confirmed.” This trial will evaluate the ability of the study device to accurately distinguish between functioning (flowing) and non-functioning (non-flowing) shunts.

Clinical staff will be required to complete training on the protocol and device measurement procedures as well as complete a roll-in study device measurement prior to enrolling main study patients.

#### Statistical Procedures:

The co-primary endpoints for this study are sensitivity and specificity. Performance measures (sensitivity, specificity, accuracy, positive predictive value (PPV), and negative predictive value (NPV)) will be estimated along with 95% two-sided confidence intervals (CI).

To calculate the performance measures, the study device output of either “flow confirmed” or “flow not confirmed” and the standard-of-care clinical treatment will place each patient into one of the following categories:

True Positive (TP): Device outputs “flow not confirmed” AND a shunt revision surgery with confirmed shunt failure is performed

False Positive (FP): Device outputs “flow not confirmed” AND either no shunt revision surgery is performed for 7 days or a shunt revision surgery without a confirmed shunt failure is performed

True Negative (TN): Device outputs “flow confirmed” AND either no shunt revision surgery is performed for 7 days or a shunt revision surgery without a confirmed shunt failure is performed

False Negative (FN): Device outputs “flow confirmed” AND a shunt revision surgery with confirmed shunt failure is performed

If a patient does not fall within one of these categories (e.g., if shunt patency was not assessed during revision surgery), data for that patient will not be included in the endpoint calculation. Study device sensitivity will be calculated as  $TP / (TP + FN)$  and study device specificity will be calculated as  $TN / (TN + FP)$ .

A minimum of 30 “positive” patients (those who undergo shunt revision surgery with a confirmed shunt failure) will be enrolled.

Secondary subgroup analyses will be performed to report on any variation between pediatric and adult patients. Additional subgroup analyses will be performed to identify any patient characteristics that may impact device performance.

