#### Enrollment Criteria:

##### *Inclusion criteria*

1. Existing ventriculoperitoneal CSF shunt on which the patient is dependent
2. At least one symptom of shunt malfunction as determined by the investigator, such as but not limited to seizure, fever, headache, vision problems, dizziness, disorientation, confusion, vomiting, lethargy, irritability, difficulty waking or staying awake, swelling along shunt tract, enlargement of head, loss of balance, gait disturbance, and loss of sensory or motor function

3. Suspicion of shunt obstruction warrants the performance of a test for this condition in the investigator's judgement
4. Region of intact skin overlying an unambiguously identifiable chronically indwelling ventricular shunt which crosses the clavicle and is appropriate in size for application of the study device
5. Available for follow-up for up to seven days
6. Signed informed consent by patient or a parent, legal guardian, health care agent, or surrogate decision maker (according to local statutes, and collectively referred to as "surrogates" in this protocol)

*Exclusion criteria*

1. Presence of multiple shunts, or presence of more than one distal shunt catheter (regardless of function) crossing the clavicle ipsilateral to the shunt with suspected obstruction
2. Use of the study device would interfere with standard patient care, or emergency surgery that cannot be delayed
3. Presence of an interfering open wound or edema over any portion of the shunt
4. Patient-reported history of adverse skin reactions to adhesives
5. Investigator judges that the subject is likely to be lost to follow-up due to unavailability or clinical outcome being unobtainable
6. Participation in the study will interfere with, or be detrimental to, administration of optimal health-care to the subject
7. Prior enrollment in this study (multiple main study enrollments of the same patient are disallowed)
8. Participation in any other investigational procedural, pharmaceutical, and/or device study that may influence the collection of valid data under this study

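### Does the plan need a rule for which revision counts when a patient has more than one within 7 days?

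*Combined protocol and SAP*

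**What the plan says.** Statistical Procedures says that the device output and the standard-of-care treatment "will place each patient into one of the following categories". TP and FN share one reference condition: "a shunt revision surgery with confirmed shunt failure is performed". FP and TN share the other: "either no shunt revision surgery is performed for 7 days or a shunt revision surgery without a confirmed shunt failure is performed". The fallback excludes some patients from the endpoint calculation; its condition begins "If a patient does not fall within one of these categories (e.g., if shunt patency was not assessed during revision surgery". The minimum of 30 positive patients is defined as "those who undergo shunt revision surgery with a confirmed shunt failure".

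Study Design says that subjects "will be followed for 7 days to determine if a revision was performed to repair or replace the existing shunt", and then: "In subjects undergoing a revision, intraoperative assessment of shunt functionality will establish the presence or absence of a complete shunt obstruction". Inclusion criterion 5 reads "Available for follow-up for up to seven days". The Scientific Abstract and the Lay Abstract repeat the 7-day follow-up for revision.

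**The concern.** The plan intends one cell per patient, but the definitions do not guarantee it. Each refers to a revision without saying first, any or last. A patient operated on twice, with failure confirmed at one operation and not at the other, satisfies both reference conditions. The fallback does not help, because it deals with patients who fit no cell, not with those who fit two.

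Two related points add to the impression of a gap:

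- The 7-day limit is attached only to the no-surgery part of FP and TN. Read literally, a patient with no revision by day 7 and a confirmed failure on day 10 also fits two cells.
- If patency is not assessed at a first revision but is assessed at a second, the fallback's example suggests exclusion, while the second operation fits a cell.

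Both co-primary endpoints, the secondary performance measures and the count of 30 positives use these cells. With sensitivity resting on perhaps 30 patients, case-by-case assignment looks like an avoidable choice within a co-primary endpoint. A further worry is that the reference finding may come up to 7 days after the measurement, with no planned analysis of whether sensitivity depends on that delay.

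**Working it through.** **Step 1: apply the cell definitions literally.** No figure in the plan can be reproduced here: the 30 positives come with no performance goal, expected sensitivity or precision target. The check is therefore on the definitions. The table shows the result with the surgery conditions as written and with a 7-day window added.

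| Revision history | As written | With 7-day window |
|---|---|---|
| None | FP or TN | same |
| One, failure confirmed, day 1 | TP or FN | same |
| One, failure not confirmed, day 1 | FP or TN | same |
| One, patency not assessed, day 1 | no cell | same |
| Two within 7 days, discordant, either order | TP+FP or FN+TN | same |
| Not assessed day 1, confirmed day 5 | TP or FN | same |
| First revision day 10, confirmed | TP+FP or FN+TN | FP or TN |

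Where one cell is shown for each device result, the device result decides between the two. With at most one revision inside 7 days and none later, every patient lands in one cell or, if patency was not assessed, in none. The overlap needs either a revision after day 7 or two discordant revisions within 7 days.

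**Step 2: see what the rest of the document settles.**

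- *Window.* Study Design, both abstracts and inclusion criterion 5 all work with a 7-day follow-up. A day-10 operation lies outside it, so the last row of the table is a wording gap.
- *Which revision.* Study Design refers to repair or replacement of the existing shunt. That is the shunt on which the device was applied. Once it has been repaired or replaced, a second operation generally examines an altered system. The natural reading is the first revision within 7 days.
- *First revision not assessed.* Under that reading the patient is excluded, in line with the fallback's own example. This could cost a positive if a later operation confirmed failure.

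The overlap is always within one device result (TP with FP, or FN with TN). An analyst can therefore settle reference status from the surgical record alone, without using the device output.

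**Step 3: size the effect.** Assumed base case: sensitivity 24/30 = 80.0% (exact 95% CI 61.4 to 92.3) and specificity 64/80 = 80.0% (69.6 to 88.1). The 30 is the plan's minimum. The 80 negatives, the 80% performance and the exact (Clopper-Pearson) method are assumptions, since the documents give none of them. Add one dual-status patient:

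| Device result | Scored as | Changed estimate | Shift (points) |
|---|---|---|---|
| Flow not confirmed | TP | sensitivity 25/31 = 80.6% | +0.6 |
| Flow not confirmed | FP | specificity 64/81 = 79.0% | −1.0 |
| Flow confirmed | FN | sensitivity 24/31 = 77.4% | −2.6 |
| Flow confirmed | TN | specificity 65/81 = 80.2% | +0.2 |

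All four values lie well inside the base-case intervals.

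For a second base, assume 27/30 and 108/120. Here 120 negatives is an upper bound with 30 positives, because the maximum of 150 includes roll-in subjects. Reclassifying one patient from FN to TN gives sensitivity 27/29 = 93.1% and specificity 109/121 = 90.1%. Reclassifying one from TP to FP gives 26/29 = 89.7% and 108/121 = 89.3%.

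**Step 4: consider an analysis by time to revision.** Restricting sensitivity to positives revised soon after measurement would resolve no dual-status patient, and the documents offer no cutoff. It would also widen the interval. At an observed 80%, the exact 95% CI is 59.3 to 93.2 with 25 positives and 56.3 to 94.3 with 20, against 61.4 to 92.3 with 30. The primary result would not change.

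**The case for a change.** The strongest case for acting is that the defect is literal and no sentence removes it. The existing-shunt wording in Study Design is a pointer, not a stated rule. The definition of a positive patient could equally be read as any confirmed failure, which competes with the first-revision reading. Exclusion criterion 7 bars repeat enrolment, not repeat surgery. Surgical records may be collected under Study Procedures, so a later operation could come to light. In the 27/30 example, moving one patient out of the positives leaves 29, below the stated minimum. Two such moves from FN to TN would raise sensitivity to 27/28 = 96.4%, and three to 27/27 = 100%. One sentence would close the matter.

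The literal overlap stands, and so does the observation that first revision is inferred. The larger shifts do not carry weight: they need two or three dual-status patients among about 30 positives, all with the device reading flow confirmed, and nothing in the documents suggests that number. The shortfall to 29 arises only if enrolment stops at exactly 30 and one of those is a dual-status patient. An explicit sentence would do no harm, but it would only write down the reading that Study Design already supports.

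**Conclusion.** No change to the plan is called for. The cell definitions overlap on paper for a patient with two discordant revisions within 7 days, but Study Design supplies the window and points to the first revision of the measured shunt, so analysts can be expected to fill the gap sensibly. One such patient moves an estimate by 0.2 to 2.6 points on the assumed 24/30 and 64/80 base, and by up to 3.1 points (90.0% to 93.1%) when one patient is reclassified on the assumed 27/30 base. Either is small beside an interval for sensitivity that runs about 31 points (61.4 to 92.3) at 24/30.

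This conclusion rests on two judgements: that discordant repeat revisions within 7 days are uncommon, for which the documents give no frequency, and that the existing-shunt wording is read in its natural sense. The missing 7-day limit in the surgery conditions is a drafting gap. An analysis by time to revision is an optional addition that would leave the primary result as it is.

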#### Research Questions(s)/Hypothesis(es):

Primary objectives: The primary objectives of this study are to determine the sensitivity and specificity of the study device for identifying the presence or absence of complete shunt failure in symptomatic hydrocephalus patients with CSF shunts.

Secondary objectives: The secondary objectives of this study are to determine the accuracy, positive predictive value (PPV), and negative predictive value (NPV) of the study device in this population. Additional objectives include collecting and describing clinical, demographic, and hydrocephalus (e.g., etiology, shunt system type, shunt system brand, shunt valve settings) characteristics of the study population, device user feedback, and shunt testing data (e.g., imaging studies). Additional study device diagnostic and performance data (e.g., temperature data and error codes) will be collected for adjudication and review purposes. The diagnostic performance of an additional flow

assessment algorithm will also be assessed using the data acquired in this study by the study device.

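### Can the trial reach 30 confirmed failures within its cap of 150 subjects, and must the plan say what happens if it does not?

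*Combined protocol and SAP*

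**What the plan says.** The Statistical Procedures section makes sensitivity and specificity co-primary, to be estimated with two-sided 95% confidence intervals. Its only size commitment is "A minimum of 30 “positive” patients (those who undergo shunt revision surgery with a confirmed shunt failure) will be enrolled".

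Study Design describes a "single-arm observational study of up to 150 (roll-in and main study) subjects at up to 10 trial sites". It requires clinical staff to "complete a roll-in study device measurement prior to enrolling main study patients", but does not say how many roll-ins there will be or whether they can count toward the 30. Patients "will be recruited by the clinical investigators based on the inclusion and exclusion criteria".

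A patient who fits none of the four outcome categories is dropped: "data for that patient will not be included in the endpoint calculation".

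The secondary objectives, under Research Questions/Hypotheses, are to "determine the accuracy, positive predictive value (PPV), and negative predictive value (NPV) of the study device in this population".

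The documents do not give an expected rate of confirmed failure, a minimum number of negatives, a rationale for 30 or 150, a rule for ending enrolment between the floor and the cap, or a statement of which limit governs if they collide.

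**The concern.** The sponsor controls how many subjects enter but not how many turn out positive. A positive is defined by revision surgery and its intraoperative finding, which come after enrolment. A floor on positives and a cap on subjects therefore jointly imply a minimum failure rate, and the plan does not show that the rate is expected to be that high. The entry criteria give some reason for caution: symptoms are described as non-specific, one symptom plus a judgement that testing is warranted is enough, and emergency surgery that cannot be delayed is excluded.

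If positives ran short, the trial would have to miss its stated minimum, raise its cap, or tilt recruitment toward patients likely to go to surgery. The last would matter most. Positive and negative predictive values and accuracy depend on the failure rate in the sample, and consecutive enrolment is not required. If instead the rate were high and enrolment stopped at the 30th positive, specificity could rest on few negatives.

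**Working it through.** **Inputs from the documents.** Floor of 30 positives and two-sided 95% intervals (Statistical Procedures); cap of 150 subjects including roll-ins, and at most 10 sites (Study Design).

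**Assumptions, because the documents give no figure.** Roll-ins total 0, 10, 20 or 30 (none to three per site at 10 sites) and do not count toward the 30. The true confirmed-failure rate p ranges from 15% to 35%. The number of positives among n main-study patients is binomial. All n are evaluable unless stated.

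The figures 30 and 150 cannot be reproduced, since no target precision, power or failure rate is given from which to derive them.

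**Step 1: break-even share, 30/n.**

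- No roll-ins: 30/150 = 20.0%
- 10 roll-ins: 30/140 = 21.4%
- 20 roll-ins: 30/130 = 23.1%
- 30 roll-ins: 30/120 = 25.0%

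Only the first follows from the documents alone. If 10% of patients were also non-evaluable, the two ends would become 30/135 = 22.2% and 30/108 = 27.8%.

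**Step 2: chance of at least 30 positives, P(Bin(n, p) ≥ 30).**

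| n | p = 15% | 20% | 25% | 30% | 35% |
|---|---|---|---|---|---|
| 150 | 5.9% | 53% | 94% | 99.8% | >99% |
| 140 | 2.6% | 37% | 86% | 99% | >99% |
| 130 | 1.0% | 22% | 72% | 97% | >99% |
| 120 | 0.3% | 11% | 54% | 90% | 99% |

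The answer turns almost entirely on p. At 30% or more the floor and cap are comfortably compatible; at 15% they are not.

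**Step 3: what a shortfall costs.** Take the pessimistic case p = 15% with n = 140. Expected positives are 0.15 × 140 = 21. Exact (Clopper-Pearson) 95% intervals for a sensitivity near 90%:

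- 27/30: 73.5% to 97.9%, about 24 points wide
- 19/21: 69.6% to 98.8%, about 29 points wide

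The loss is about 5 points of width, and it is visible in the reported interval.

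**Step 4: specificity.** An interval of 65.4% to 90.4% (36/45, 25 points wide) arises only if the failure rate is 40% and enrolment ends at the 30th positive, that is, after 30/0.40 = 75 patients. The plan states a minimum for positives, not a stopping point. At the same 40% rate with 140 main-study patients, expected negatives are 0.60 × 140 = 84, and 67/84 gives 69.6% to 87.7%, about 18 points wide.

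**Step 5: predictive values under selection.** Assume sensitivity 90% and specificity 80%. Then PPV = 0.9p / (0.9p + 0.2(1 − p)):

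- p = 15%: 0.135 / (0.135 + 0.170) = 44%
- p = 21.4%: 55%
- p = 25%: 0.225 / (0.225 + 0.150) = 60%

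Over the same range NPV = 0.8(1 − p) / (0.8(1 − p) + 0.1p) moves only from 97.8% to 96.0%. The PPV shift of 11 to 16 points requires a true rate of 15%, the assumed accuracy figures, and recruitment tilted just far enough to meet the floor. It also holds sensitivity and specificity fixed under that tilt. None of these comes from the documents.

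**The case for a change.** The strongest case for a change is that the floor of 30 is the only size the plan promises, and it rests on a rate nobody has written down. At a true rate of 20%, which is exactly break-even if every place went to the main study, the chance of 30 positives is only 53%, falling to 37% with 10 roll-ins. An 80% chance needs a true rate of about 22.6% with 150 main-study patients, 24.1% with 140 or 28.1% with 120, and non-evaluable patients push these up further. The plan would be clearer if it gave an expected rate, the number of roll-ins and whether they count, and which limit governs. All of that stands, as a remark on missing detail.

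Three parts do not stand.

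- The entry criteria do not show that the rate is low. They also restrict the trial to shunt-dependent, symptomatic patients in whom suspected obstruction warrants a test, and the background says shunts often fail. The documents leave the rate open in both directions.
- Nothing suggests that sites would favour surgical candidates. Recruitment is tied to the inclusion and exclusion criteria. A shortfall could also be met by amending the cap or by reporting fewer positives, so selection is not the only way out.
- Subtracting roll-ins one for one is not established either. The exclusion for prior enrolment rules out repeat main-study entries, which may leave room for a roll-in patient to enter the main study later.

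**Conclusion.** No change follows. The documents alone support one figure: the floor and the cap can both hold only if at least 20% of subjects have a confirmed failure. Higher thresholds, up to 25% or 28%, depend on assumed numbers of roll-ins and non-evaluable patients. Whether the threshold is met depends on a rate the documents do not give, so this is a dependency and not an inconsistency.

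Followed as written, the plan still gives sound results. With enrolment on the stated criteria, sensitivity and specificity are estimated validly at any failure rate. The aim is estimation, with no performance goal, hypothesis test or power claim for a shortfall to break. In the pessimistic case (15% failure rate, 140 main-study patients) the sensitivity interval widens by about 5 points and the report would show it.

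The possible remedies add little. Writing down an expected rate and a governing limit fills in detail that the sponsor can settle during conduct. Raising the cap in advance buys certainty with more subjects: at a 20% rate, an 80% chance of 30 positives needs 170 main-study patients, or 180 to 200 in total with 10 to 30 roll-ins, which is 30 to 50 above the cap. Reporting predictive values next to the sample failure rate adds nothing that the four outcome counts do not already show. A consecutive-enrolment rule and log would guard against a selection problem for which the documents give no evidence.

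### Patients without a device output would drop out of both co-primary estimates, and the plan has no supplementary estimate showing how far this could move sensitivity or specificity

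*Combined protocol and SAP*

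**What the plan says.** All the relevant rules are in the Combined protocol and SAP. Under Statistical Procedures, the device output and the clinical outcome together "will place each patient into one of the following categories". A true positive is defined as "Device outputs “flow not confirmed” AND a shunt revision surgery with confirmed shunt failure is performed" and a false negative as "Device outputs “flow confirmed” AND a shunt revision surgery with confirmed shunt failure is performed". The false-positive and true-negative definitions also each start from one of the two outputs. Sensitivity is TP/(TP+FN) and specificity is TN/(TN+FP).

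For a patient who fits none of the four, "data for that patient will not be included in the endpoint calculation". The one example given is a reference-standard gap (patency not checked at revision), but it is introduced as an example, so the rule also covers a missing device output.

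The enrolment minimum is worded differently. It asks for at least 30 positive patients, described as "those who undergo shunt revision surgery with a confirmed shunt failure) will be enrolled". It rests on the surgical outcome alone. Study Design describes a "single-arm observational study of up to 150 (roll-in and main study) subjects at up to 10 trial sites".

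Under Research Questions/Hypotheses, the secondary objectives mention further device data: "e.g., temperature data and error codes) will be collected for adjudication and review purposes". No report or analysis of those codes is attached.

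**The concern.** A diagnostic study can lose patients on either side of the comparison: the reference standard may be missing, or the device may give no usable result. The plan removes both kinds, but the second kind matters in its own way. If the device cannot classify some patients, sensitivity among those it can classify is a narrower quantity than sensitivity in the symptomatic patients named in the primary objectives. The two are close if no-output patients are rare or would have been classified about as well as the rest. They can differ visibly otherwise, because with about 30 positives each patient is worth about 3 percentage points.

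The plan promises neither a count of such patients nor an estimate that includes them. A reader of the results could not tell whether 24 of 27 means 27 positives or 30 positives with three unread. The same applies to specificity.

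**Working it through.** **Step 1: the definitions side by side.** Take a patient with confirmed failure at surgery and no device output.

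| Rule | Is the patient counted? |
|---|---|
| Minimum of 30 positives (surgery with confirmed failure) | Yes |
| TP or FN (confirmed failure and one of two outputs) | No |
| Sensitivity, TP/(TP+FN) | No, dropped |

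A patient without confirmed failure and without an output is dropped from TN+FP, and so from specificity, in the same way.

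**Step 2: the plan's own figure.** The 30 cannot be reproduced, because the documents give no expected sensitivity, performance goal, power or target interval width. The interval method is not stated either; exact (Clopper-Pearson) intervals are used below.

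**Step 3: formulas.** Let m be the positives without an output and N = TP+FN+m.

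- As the plan reports: TP/(TP+FN)
- No-output counted as incorrect: TP/N
- No-output counted as correct: (TP+m)/N

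The two bounds lie m/N apart.

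**Step 4: sensitivity.** Inputs: N = 30 from the plan's minimum. The documents give no no-output rate, so m = 1, 2, 3 or 5 is assumed, with 3 misses assumed among patients who have an output.

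| m | Reported | As incorrect | As correct |
|---|---|---|---|
| 1 | 26/29 = 89.7% | 26/30 = 86.7% | 27/30 = 90.0% |
| 2 | 25/28 = 89.3% | 25/30 = 83.3% | 27/30 = 90.0% |
| 3 | 24/27 = 88.9% | 24/30 = 80.0% | 27/30 = 90.0% |
| 5 | 22/25 = 88.0% | 22/30 = 73.3% | 27/30 = 90.0% |

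Exact 95% intervals for m = 3: reported 70.8-97.6%; as incorrect 61.4-92.3%; as correct 73.5-97.9%. The constant 90.0% in the last column follows from fixing the misses at 3.

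**Step 5: specificity.** Assume 100 patients without confirmed failure, 10 of them without an output, and 81 of the other 90 correct. Reported: 81/90 = 90.0%. As incorrect: 81/100 = 81.0%. As correct: (81+10)/100 = 91.0%.

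**Step 6: precision alone.** At 90% sensitivity the exact lower limit is 73.5% with 30 positives (27/30) and about 72.3% with 27 (interpolated at 24.3/27). The smaller denominator costs little; the possible shift in the estimate in Step 4 is the larger matter.

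**Step 7: the cap of 150.** If all 150 could count, 30 positives would need 30/150 = 20.0% of subjects to be positive. Roll-in subjects share the cap, so 20.0% is a lower bound. If, say, 10 roll-ins were not counted, the figure would be 30/140 = 21.4%. The documents give neither a roll-in number nor a positive rate, and do not say whether roll-ins enter the endpoint.

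**The case against.** The strongest reply is that the case may never arise. The plan expects one of two outputs to place every patient, and the flow-not-confirmed label could be read as covering any measurement that fails to show flow. Nor is a repeat measurement ruled out. This stands as far as it goes: a reader might infer from the collection of error codes that unread patients will occur, but the documents do not say that an error leaves a patient without an output. They do not exclude it either, and the drop rule itself allows for patients who fit no category.

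Second, the handling is pre-specified. That also stands. It would be wrong to say the plan has no rule for a missing output; it has one, and accuracy among classified patients is a well-defined measure. What is absent is anything that shows how much depends on the rule.

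Third, counting every unread patient as incorrect is an extreme bound. It is, and in every sensitivity case shown above the reported figure is nearer to the as-correct bound than to the as-incorrect one. The bounds are a range to report beside the primary estimate, not a replacement for it.

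Fourth, a reader might infer that the study would miss its minimum of 30 or needs more patients. The documents do not support that. The 30 is an enrolled count, which the plan would still meet; it is a minimum that may be exceeded; and no stated criterion depends on it.

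**Conclusion.** The point holds as a low-cost improvement to the analysis, not as an error in the primary calculation. Followed as written, the drop rule makes sensitivity and specificity describe only patients with one of the two outputs, and no planned estimate shows the possible effect of the others.

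The size is unknown. On the assumed figures it runs from negligible to material: with 1 unread positive of 30, the bounds are 86.7% and 90.0% around a reported 89.7%; with 3, they are 80.0% and 90.0% around 88.9%. These rest on assumed no-output counts and an assumed 3 misses. If no patient lacks an output, nothing changes.

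The gap between enrolled and evaluable positives is secondary. TP+FN may fall below 30, with little loss of precision, and this gives no ground for a larger enrolment. The reporting gap would remain even if TP+FN reached 30.

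**What to change.** Leave the primary calculation as it stands and add the following to Statistical Procedures, before device results are unblinded:

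1. Report the number of confirmed-failure patients without an output beside sensitivity, and the number of patients without confirmed failure and without an output beside specificity.
2. Add two supplementary estimates of each measure, with 95% intervals: one counting these patients as incorrect, one counting them as correct.
3. Report the evaluable number of positives (TP+FN) beside the enrolled number, making clear that the 30 is an enrolled count.

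A sentence saying what output, if any, an error code gives would help a reader apply these rules.

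The cost is a little more analysis on data already collected, with no extra patients. The one real downside for the sponsor is that the as-incorrect bound may be less favourable than the primary estimate.
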